5.7 Criteria for Taking a Participant Off Study

Participants will be removed from study when any of the following criteria apply:

- Lost to follow-up
- Withdrawal of consent for data submission
- Death

The reason for taking a participant off study, and the date the participant was removed, must be documented in the CRF.

The research team will update the relevant Off Study information in OnCore.

6. DOSING DELAYS/DOSE MODIFICATIONS

Dose delays and modifications will be made as indicated in the following sections. The descriptions and grading scales found in the revised NCI Common Terminology Criteria for Adverse Events (CTCAE) version 4.0 will be utilized for dose delays and dose modifications. A copy of the CTCAE version 4.0 can be downloaded from the CTEP website at: http://ctep.cancer.gov/protocolDevelopment/electronic_applications/ctc.htm.

6.1 Expected Toxicities

The table below summarizes treatment-emergent AEs considered expected for prexasertib (LY2606368) serious adverse reaction reporting.

Table 4: Toxicities Considered Expected	
System Organ Class	Event Preferred Term
Blood and lymphatic system disorders	Neutropenia (including neutrophil count decreased)
	Thrombocytopenia (including platelet count decreased)
	Anemia (including hemoglobin and hematocrit decreased)
	Leukopenia (including white blood cell count decreased)
	Febrile neutropenia
	Lymphopenia (including lymphocyte count decreased)
Infections and infestations	Sepsis (including urosepsis)

6.2 Specific Toxicity Management

6.2.1 Hematologic Toxicity Management

6.2.1.1 Neutropenia

Neutropenia has been the most frequent and severe toxicity following treatment with prexasertib (LY2606368) every 14 days, with grade 3 or greater decreases in neutrophil count deemed related to prexasertib treatment having been observed in approximately three-quarters of patients. In general, neutrophil counts nadir on day 8 and grade 4 decreases are often transient (e.g., less than 5 days). Febrile neutropenia has been reported in approximately 11% of patients, but no patients have died due to febrile neutropenia. Please refer to **Section 5.4.1** for G-CSF guidelines.

Table 5: Management of Neutropenia	
Toxicity	Prexasertib Dose Management
Uncomplicated Grade 3 Neutropenia (ANC < 1 K/uL)	Hold infusion until recovery to grade 2, resume at same dose level.
Grade 3 Neutropenia Associated with a Fever or Infection (ANC < 1 K/uL)	Hold infusion until recovery to grade 2, resume with one dose level reduction.
Uncomplicated Grade 4 Neutropenia < 7 Consecutive Days in Duration (ANC < 0.5 K/uL)	Hold infusion until recovery to grade 2, resume at same dose level.
Grade 4 Neutropenia ≥ 7 Consecutive Days in Duration (ANC < 0.5 K/uL)	Hold infusion until recovery to grade 2, resume with one dose level reduction.

6.2.1.2 Thrombocytopenia

Grade 3 or greater thrombocytopenia has been observed in approximately one fifth of patients.

Table 6: Management of Thrombocytopenia	
Toxicity	Prexasertib Dose Management
Grade 3 Platelet Count Decrease - Not Associated with Bleeding (Platelet count 25 - 50 K/uL)	Hold infusion until recovery to grade 2, resume at same dose level.
Grade 3 Platelet Count Decrease - Associated with Bleeding (Platelet count 25 - 50 K/uL) OR Grade 4 Platelet Count Decrease (Platelet count < 25 K/uL)	Hold infusion until recovery to grade 2, resume with one dose level reduction.

6.2.1.3 Anemia

Patients should receive blood transfusions as deemed necessary in the judgment of the treating investigator. Participants may be dose reduced for anemia \geq grade 2 and considered at least possibly related to prexasertib if the treating investigator believes it to be in the best interest of the participant.

6.2.2 Non-hematologic Toxicity Management

6.2.2.1 Fatigue

Participants experiencing \geq grade 3 fatigue should have their prexasertib (LY2606368) infusion held until recovery to \leq grade 2. Upon resuming, the prexasertib dose should be reduced to the next lowest dose level unless the fatigue was attributed to anemia and has resolved following transfusion. In that case, the participant may be maintained at their current dose level if the treating investigator feels it is in the participant's best interest.

Participants with intolerable grade 2 fatigue may have their prexasertib held and/or reduced to the next lowest dose level if it is considered to be in their best interest by the treating investigator.

6.2.2.2 Nausea/vomiting

Patients experiencing nausea or vomiting should be offered appropriate supportive care, including the use of antiemetic therapy and IV hydration if needed. Participants experiencing \geq grade 3 nausea or vomiting (or intolerable grade 2) despite optimal medical management should have prexasertib dose-reduced to the next lowest dose level.

6.2.2.3 Management of Other Non-hematological Toxicity

For any other \geq grade 3 non-hematological toxicity which cannot be managed despite optimal supportive care, prexasertib should be held until recovery to \leq grade 1 or baseline. Upon resuming, prexasertib should be dose-reduced to the next lowest dose level. Exceptions include:

- Photosensitivity, rash, or neuropathy, in which cases prexasertib may be resumed upon resolution to grade 2 if deemed appropriate by the treating investigator.
- Non-clinically significant laboratory abnormalities. Prexasertib may be continued without interruption at the current dose level if deemed appropriate by the treating investigator, or may be held and/or dose reduced at the treating investigator's discretion.
- Asymptomatic laboratory abnormalities that resolve to \leq grade 1 or baseline within 48 hours of repletion. Prexasertib may be resumed at the current dose level if deemed appropriate by the treating investigator, or may be dose reduced at the treating investigator's discretion. Repletion and treatment may occur on the same day.

Patients experiencing intolerable grade 2 toxicities may have their infusion of prexasertib delayed at the treating investigator's discretion. Upon resolution, the dose of prexasertib may be reduced if the treating investigator considers a dose reduction appropriate.

6.3 Dose Modifications/Delays

Participants who are benefiting from prexasertib (LY2606368) in the opinion of the treating investigator may have their infusion held for up to 4 weeks to allow for recovery of toxicity. Participants requiring a longer hold should be removed from the trial. Exceptions to this requirement are possible should the principal investigator agree that the patient may continue despite the length of time off drug.

6.3.1 Dose Modifications

A maximum of two dose reductions are allowed. If a patient requires more than two dose reductions, they should be removed from the trial. Once a patient's dose has been reduced, it may be re-escalated to the previous dose level if the toxicity has resolved to baseline or \leq grade 1 and with agreement from the principal investigator.

Table 7: Dose Modifications	
Dose Reduction Level	Prexasertib Dose
-1	80 mg/m ²
-2	60 mg/m ²

If the study medication is placed on hold for toxicity, the counting of cycle days and assessment schedule will continue without interruption. For example, a patient who does not receive their prexasertib (LY2606368) infusion on cycle 2 day 15 due to toxicity will proceed with their next scheduled visit as previously planned (cycle 3 day 1) with additional interim visits as needed for clinical management. The cycle will not restart for dosing delays due to toxicity.

6.3.2 Overdose

There is no known antidote for over-dosage of prexasertib (LY2606368). In the case of suspected overdose, monitor hematologic parameters, serum chemistry, vital signs, cardiac function, and provide supportive care as necessary.

7. ADVERSE EVENTS: LIST AND REPORTING REQUIREMENTS

Adverse event (AE) monitoring and reporting is a routine part of every clinical trial. The following list of reported and/or potential AEs (**Section 7.1**) and the characteristics of an observed AE (**Sections 7.2 and 7.3**) will determine whether the event requires expedited reporting **in addition** to routine reporting.

7.1 Expected Toxicities

A list of the expected adverse events associated with the investigational agent administered in this study can be found in **Section 6.1**.

7.1.1 Adverse Event Characteristics

- **CTCAE term (AE description) and grade:** The descriptions and grading scales found in the revised NCI Common Terminology Criteria for Adverse Events (CTCAE) version 4.03 will be utilized for AE reporting. All appropriate treatment areas should have access to a copy of the CTCAE version 4.03. A copy of the CTCAE version 4.03 can be downloaded from the CTEP web site

http://ctep.cancer.gov/protocolDevelopment/electronic_applications/ctc.htm.

- **For expedited reporting purposes only:**
 - AEs for the agent that is listed above should be reported only if the AE varies in nature, intensity or frequency from the expected toxicity information which is provided in Section 7.1.
 - Other AEs for the protocol that do not require expedited reporting are outlined in section 7.4 - Expedited Adverse Event Reporting, under the sub-heading of Protocol-Specific Expedited Adverse Event Reporting Exclusions.

- **Attribution of the AE:**
 - Definite – The AE *is clearly related* to the study treatment.
 - Probable – The AE *is likely related* to the study treatment.
 - Possible – The AE *may be related* to the study treatment.
 - Unlikely – The AE *is doubtfully related* to the study treatment.
 - Unrelated – The AE *is clearly NOT related* to the study treatment.

7.2 Serious Adverse Events

A serious adverse event (SAE) is any adverse event that occurs after the initial dose of study treatment, during treatment, or within 30 days of the last dose of treatment that results in one of the following outcomes:

- Death
- Hospitalization for greater than 24 hours
- Prolonging an existing inpatient hospitalization
- A life-threatening experience (that is, immediate risk of dying)
- Persistent or significant disability/incapacity
- Congenital anomaly/birth defect
- Considered significant by the investigator for any other reason

Previously planned (prior to signing the informed consent form) surgeries, and non-disease related elective surgeries planned during the course of the study, should not be reported as SAEs unless the underlying medical condition has worsened or appeared during the course of the study. Events that occur prior to the first administration of study medication should not be reported as SAEs.

Preplanned hospitalizations or procedures for preexisting conditions that are already recorded in the patient's medical history at the time of study enrollment should not be considered SAEs. Hospitalization or prolongation of hospitalization without a precipitating clinical AE (e.g., for the administration of study therapy or other protocol-required procedure) should not be considered SAEs.

Important medical events that may not result in death, be life-threatening, or require hospitalization may be considered SAEs when, based on appropriate medical judgment, they

may jeopardize the patient and may require medical or surgical intervention to prevent one of the outcomes listed in this definition.

Death due to disease progression should not be reported as an SAE unless the investigator deems it to be related to the use of study drug.

Study site personnel must alert Eli Lilly of any SAE as soon as possible and no later than 24 hours of the investigator and/or institution receiving notification of the SAE experienced by a patient participating in the study. The SAE reports should be on a standard reporting form (e.g. CIOMS, MedWatch 3500a, or similar) and are to be sent to Eli Lilly via fax at [name].

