2.5.1 Collection of Fresh Tumor Tissue – Replicative Stress and HR Cohorts

In order to retrospectively explore the determinants of response and resistance to prexasertib, a mandatory pre-treatment fresh tumor biopsy will be obtained from the patients during Stage 1 of the 2-stage trial. The nine biopsies from both cohorts will be sufficient to demonstrate meaningful results, however will allow patients who are not amenable to biopsy or for whom a biopsy would pose significant risk to enroll on trial at the later stage.

Analysis of biopsy samples taken at distinct points enables addressing of key questions including the genomic lesions present in samples studied and their potential impact upon response following prexasertib therapy.

It is the anticipation that most patients on this study will have had their tumor genomically characterized by either the OncoPanel test at DFCI/BWH (a custom hybrid capture panel which via next-generation sequencing will identify mutations and copy-number alterations in cancer associated genes) or via another CLIA-certified method at the time of enrollment. A pre-

treatment tumor tissue sample will be subjected to WES at the Broad Institute Center for Cancer Precision Medicine. WES enables a comprehensive analysis of DNA mutation in human tumor samples. Gene expression profiling has been demonstrated to predict disease-free and overall survival in multiple cancers and guide future treatment decisions and biologic discovery⁵⁴⁻⁵⁶. WES will be performed to profile the HR proficiency of the tumor, and will involve up to 100 genes of interest in DNA repair in order to obtain the entire HR state. This will allow identification of further genomic alterations that may occur outside of the pre-set enrollment genetic alterations of these patients. The data obtained via WES will enable us to identify secondary alterations that may impact clinical response.

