 - AST(SGOT)/ALT(SGPT) $\leq 2.5 \times$ institutional ULN, unless liver metastases are present and then $\leq 5 \times$ institutional ULN is acceptable
 - Serum creatinine $\leq 1.5 \times$ institutional ULN
- 3.1.7 Participants enrolling to the HR or replicative stress cohorts during Stage 1 must have disease that is amenable to biopsy and be willing to undergo a pre-treatment tumor biopsy.
- 3.1.8 The potential effects of prexasertib (LY2606368) use during pregnancy and lactation are not known. Nonclinical studies of prexasertib on pregnancy and fetal development have not been performed. To minimize any potential risks, men and women with reproductive potential should use medically approved contraceptive precautions during treatment and for 3 months following the last dose of prexasertib. Should a woman become pregnant or suspect she is pregnant while she or her partner is participating in this study, she should inform her treating physician immediately. Men treated or enrolled on this protocol must also agree to use adequate contraception prior to the study, for the duration of study participation, and for 3 months after completion of prexasertib administration.
- 3.1.9 Ability to understand and the willingness to sign a written informed consent document.
- 3.1.10 QTcF value of ≤ 470 msec on screening electrocardiogram (EKG).

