3.2 Exclusion Criteria

Participants who exhibit any of the following conditions will not be eligible to participate

in the study:

- 3.2.1 Participants who have had chemotherapy, other investigational or biologic therapy, major surgery, or radiotherapy within 3 weeks (6 weeks for nitrosoureas or mitomycin C) prior to the planned first dose of prexasertib (LY2606368) therapy.
- 3.2.2 Participants who have not recovered to eligibility levels from prior toxicity or adverse events as a result of previous treatment prior to the study.
- 3.2.3 Participants who have received prior treatment with a CHK1 inhibitor.
- 3.2.4 Participants who have received prior radiation therapy to > 25% of the bone marrow.
- 3.2.5 Participants with known untreated brain metastases should be excluded from this clinical trial because of their poor prognosis and because they often develop progressive neurologic dysfunction that would confound the evaluation of neurologic and other adverse events. Participants with a history of brain metastases that have been treated, are no longer taking corticosteroids, and have been stable on imaging for at least one month following the end of treatment are permitted.
- 3.2.6 History of allergic reactions attributed to compounds of similar chemical or biologic composition to prexasertib.
- 3.2.7 Participants with a personal or family history of long QT syndrome.
- 3.2.8 Uncontrolled intercurrent illness including, but not limited to, ongoing or active infection, NYHA Class III/IV heart failure, unstable angina pectoris, cardiac arrhythmia, myocardial infarction within 3 months of enrollment, or psychiatric illness/social situations that would limit compliance with study requirements.
- 3.2.9 Pregnant or breastfeeding females. The potential effects of prexasertib use during pregnancy and breastfeeding are not known and prexasertib has the potential for teratogenic or abortifacient effects.
- 3.2.10 Known HIV-positive participants are ineligible because these participants are at increased risk of lethal infections when treated with marrow-suppressive therapy. Appropriate studies will be undertaken in HIV-positive participants when indicated.
- 3.2.11 Participants enrolling to the HR or replicative stress cohort during Stage 1 may not be on anticoagulant therapy unless the treating investigator has deemed it safe to temporarily hold to facilitate the pre-treatment tumor biopsy.

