4. REGISTRATION PROCEDURES

4.1 General Guidelines for DF/HCC Institutions

Institutions will register eligible participants in the Clinical Trials Management System (CTMS) OnCore. Registrations must occur prior to the initiation of protocol therapy. Any participant not registered to the protocol before protocol therapy begins will be considered ineligible and registration will be denied.

An investigator will confirm eligibility criteria and a member of the study team will complete the protocol-specific eligibility checklist.

Following registration, participants may begin protocol therapy. Issues that would cause treatment delays should be discussed with the Overall Principal Investigator (PI). If a participant does not receive protocol therapy following registration, the participant's registration on the study must be canceled. Registration cancellations must be made in OnCore as soon as possible.

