9. BIOMARKER, CORRELATIVE, AND SPECIAL STUDIES

9.1 Biomarker Studies

9.1.1 Exploratory Tumor Biopsy – Replicative Stress and HR Cohorts

Mandatory fresh tumor biopsies will be obtained from the patients enrolled to the replicative stress or HR cohorts during Stage 1 of the 2-stage trial. The biopsies will be obtained at baseline (any time prior to the first infusion).

Core biopsy samples should be obtained for analysis. Three-to-four biopsy passes utilizing a 16-18 gauge needle are preferable, but a 20 gauge core needle biopsy is also acceptable. Less than the goal amount of tissue is acceptable for the biopsy procedure, and should be based upon the clinical judgment of the treating investigator and the clinician performing the procedure.

Biopsy samples should be fresh frozen. A plastic cryomold should be labeled with the protocol number, study subject number, and the exact date and time of collection. Several drops of OCT compound will be placed into the cryomold and at time of biopsy the sample will be placed into OCT, covered with additional drops of OCT and then placed upon dry ice immediately. The specimen will then be stored at -80°C until used.

The frozen samples should be shipped to the Broad Institute Center for Cancer Precision Medicine. The baseline tumor tissue sample should be shipped at the same time as the germline blood sample as described below in **Section 9.1.3**.

Biopsy samples should be sent on dry ice to:

Broad Institute Center for Cancer Precision Medicine
[name]
ATTN: Samples Lab
[name]

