13.5 Reporting and Exclusions

13.5.1 Evaluation of Toxicity

All participants will be evaluable for toxicity from the time of their first treatment.

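### Serious complications of the mandatory Stage 1 biopsy (HR and replicative stress cohorts) that begin before the first infusion are kept out of SAE reporting

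*Combined protocol and SAP*

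**What the plan says.** **The biopsy.** Section 9.1.1 states: "Mandatory fresh tumor biopsies will be obtained from the patients enrolled to the replicative stress or HR cohorts during Stage 1". On timing it says: "The biopsies will be obtained at baseline (any time prior to the first infusion". Section 3.1.7 makes it a condition of entry: "Participants enrolling to the HR or replicative stress cohorts during Stage 1 must have disease that is amenable to biopsy". The tissue goes to whole exome sequencing, which is an exploratory objective (1.4) and is performed retrospectively (13.4). The protocol is aware of the risk. Section 2.5.1 lets patients "for whom a biopsy would pose significant risk" enter at the later stage, and exclusion 3.2.11 bars patients on anticoagulants "unless the treating investigator has deemed it safe to temporarily hold to facilitate the pre-treatment tumor biopsy".

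**The safety rules.** Section 7.2 defines an SAE as arising after the initial dose and up to 30 days after the last, and then instructs: "Events that occur prior to the first administration of study medication should not be reported as SAEs". Section 7.3.1 uses the same window for reports to the Overall PI. The 24-hour alert to the drug supplier in 7.2 applies to SAEs, so it has the same limits. In Table 10 the biopsy is marked at screening, and the adverse event row is first marked at cycle 1 day 1. Section 13.5.1 says: "All participants will be evaluable for toxicity from the time of their first treatment". Section 13.3 restricts the toxicity analysis to patients who received study drug. Under 4.1, if a registered participant is not treated, "the participant's registration on the study must be canceled".

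**The concern.** The biopsy is compulsory for these participants and has no stated role in their treatment. The period in which its complications are most likely to appear, between the procedure and the first infusion, is the period that 7.2 removes from SAE reporting. This is a stated rule, not a gap that a site could fill by ordinary good practice: a site following 7.2 literally would not file the report.

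What is at stake is oversight. The Overall PI and the safety committee need to see serious harm from a required non-therapeutic procedure if they are to judge whether it should stay compulsory. The most serious case, a complication that prevents treatment, has the weakest route into the study record.

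**Working it through.** The plan states no figure on this point, so the main check is to follow one hypothetical event through the text: a serious complication with onset after the biopsy and before the first infusion, in a Stage 1 HR participant.

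1. *Is it an SAE?* No. It precedes the initial dose (7.2), and the pre-dose sentence has no exception. The one mention of protocol-required procedures in 7.2 is a further exclusion, for hospital stays with no clinical event behind them. It says nothing about complications.
2. *Must it go to the Overall PI on an expedited basis?* No. Section 7.3.1 uses the same window.
3. *Must the drug supplier be told?* No. That duty covers SAEs only.
4. *Can it be attributed to the biopsy?* The scale in 7.1.1 grades relation to study treatment. There is no category for a procedure.
5. *Is it in the toxicity analysis?* If the patient is never dosed, no (13.3, 13.5.1). If the patient is later dosed, the patient is in the analysis set, but 13.5.1 starts evaluation at first treatment, so inclusion of the earlier event is not assured.
6. *Does the patient stay on the study record?* If registered and never dosed, the registration is canceled (4.1).

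**How many biopsies does a change still affect?** Inputs from Sections 13 and 13.2: 9 participants per arm in Stage 1; 15 accrued in total at 5 December 2017; 10 of those in the replicative stress cohort, now closed.

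- Accrued to HR and CCNE1 together: 15 − 10 = 5. The split is not given, so HR had between 0 and 5.
- Compulsory HR biopsies remaining: from 9 − 5 = 4 to 9 − 0 = 9, before replacements.

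**Chance of at least one serious complication.** The documents give no rate. I assume 1% to 5% per biopsy, independent between patients, and use 1 − (1 − q)^n:

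| Assumed rate q | n = 4 | n = 9 |
|---|---|---|
| 1% | 1 − 0.99^4 = 3.9% | 1 − 0.99^9 = 8.6% |
| 5% | 1 − 0.95^4 = 18.5% | 1 − 0.95^9 = 37.0% |

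The range is about 4% to 37%. It counts every complication as starting before the first dose. One that starts after the infusion falls inside the SAE window, so these are upper figures for the events the rule misses.

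**The case against.** The strongest reply is that 7.2 says only that early events are not to be reported *as SAEs*; it does not say they are not adverse events. Section 7.6 requires all adverse events on the toxicity case report forms submitted to the Overall PI, and gives no start date. Section 10 requires assessments to precede any study agent, so the cycle 1 day 1 adverse event check could pick up a complication in a patient who reaches dosing. Section 4.1 asks that problems likely to delay treatment be discussed with the Overall PI. Section 7.3.2 sends adverse events to the IRB office under its own policy, 7.5 covers local risk management, and 12.2 allows the safety committee a study-team summary and further information on request.

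Much of this stands. A reader might infer that biopsy harms lie outside every collection window, or that the Overall PI and the committee could never learn of them. The documents do not support that, because the routes above exist. None of them clearly requires the event to be captured, however. Section 7.6 does not mention procedures or the pre-dose period; the day 1 check never happens for a patient who is not dosed; the 4.1 discussion concerns delay and creates no safety record; and what the IRB policy demands cannot be seen from the protocol.

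Other stronger readings also fail. The biopsy is not the only research procedure, since 9.1.2 also requires research blood samples. Three to four core passes are a preference, and less tissue is accepted. Sections 2.5.1 and 3.2.11 reduce the risk as well as acknowledging it. Counting all 2 × 9 = 18 planned biopsies would give up to 1 − 0.95^18 = 60%, but that includes a closed cohort that no amendment can reach.

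**Conclusion.** The point holds in a limited form. For Stage 1 participants in the HR and replicative stress cohorts, a serious biopsy complication with onset before the first infusion is excluded by rule from SAE reporting and from expedited notice to the Overall PI and the drug supplier. If the patient is never dosed, it is also outside the toxicity analysis. Capture as a routine adverse event is possible but not assured. This conclusion rests on the text alone and does not depend on any complication rate.

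The forward-looking size is modest: about 4 to 9 HR biopsies at 5 December 2017, before replacements, with a chance of at least one serious complication of about 4% to 37% under the assumed 1% to 5%. The primary endpoint, the two-stage rule, alpha and power are unaffected. A change is still worth making, because the procedure is compulsory and non-therapeutic and the remedy is small.

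**What to change.** - **Section 7.2, with 7.3.1 aligned:** keep the pre-dose exclusion for drug-related SAE reporting, but except serious events related to a protocol-required procedure, including the Stage 1 biopsy and any anticoagulation hold for it. Require these to be recorded and reported to the Overall PI from the start of the procedure.
- **Table 10:** add an entry for procedure-related events at the biopsy visit, with a matching line on the case report form.
- **Section 4.1:** state that such events stay on file even if registration is canceled.
- **Reporting:** list them separately, for all biopsied participants whether dosed or not, so that the drug-toxicity denominator in 13.3 and 13.5.1 is unchanged.

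The cost is a short text change, one calendar entry, one form line and a few extra reports during screening. It adds no procedure and no patients.
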